2 SYNOPSIS

Title of study	Awake PRO ne Positioning in PatientS with Acute Hypoxemic Respiratory Failure in Germany – A Randomized Controlled Study
Coordinating Principal Investigator	Acronym: PROSA [name]
Deputy-PI Study coordinator	[name], MBA
Deputy study coordinator	[name]
Trial manager	[name], PhD, MBA
Study centre	University Medical Center Hamburg-Eppendorf Department of Intensive Care Medicine [name], Germany
Clinical Trials-No.	N/A
Study Period	First patient in to last patient out (months): 18.0 Duration of the entire trial (months): 30.0 (6 months preparation, 18 months trial conduction, 6 months reporting) Recruitment period (months): 18 FPFV: Q2/2025 LPLV: Q4/2026
Phase of development	Phase 4
Medical condition	Acute Hypoxemic Respiratory Failure due to Pneumonia
Objective(s)	
 i. To evaluate if the application of standard awake prone positioning in spontaneous breathing patients (defined as patients without invasive mechanical ventilation or extracorporeal respiratory support) with acute hypoxic respiratory failure due to pneumonia at the intensive care unit (ICU) is superior to standard supine/semi-recumbent position in reduction of the rate of tracheal intubation and/or all-cause death within 28 days after randomization. ii. To assess safety and tolerability of awake prone positioning in patients with acute hypoxic respiratory failure due to pneumonia on the ICU.
Hypothesis	Prone positioning has shown beneficial effects in intubated patients with severe respiratory failure and positive effects in awake patients with COVID-19 pneumonia. Since the pandemic the rate of awake prone positioning has increased and became a standard medical therapy in ICUs worldwide. Conclusive evidence for patients with AHRF without COVID-19 is still missing. We hypothesis that awake prone position in patients with AHRF is beneficial in terms of reducing the rate of tracheal intubation and/or all-cause death.
Intervention	
Intervention:
 
 - Standard Awake Prone Positioning as defined by the study manual for a length of at least 72 hours

	
Control:
 
- Standard positioning (supine/semi-recumbent) (alone) of patients with acute hypoxemic respiratory failure according to the usual practice of each participating centre
 
Follow-up per patient:
 
Follow-up for all patients will be 28 days.


Key inclusion and exclusion criteria
	
Key inclusion criteria:
 
 • Patients in the intensive care unit • High possibility of Pneumonia (community-acquired pneumonia or hospital-acquired pneumonia) either diagnosed by chest x-ray or computed tomography or clinically diagnosed at least with one of the following signs 
 ◦ Appearance of purulent secretions or changes in characteristics (color, odor, quantity, consistency) ◦ Cough or dyspnea or tachypnea ◦ Evocative auscultation • Presence of acute hypoxemic respiratory failure ($\text{PaO}_2/\text{FiO}_2 \leq 300 \text{ mmHg}$ or $\text{SpO}_2/\text{FiO}_2 \leq 315$) 
 ◦ with need for supplementary oxygen via HFNO, NIV or CPAP with at least 40% FiO_2 
Key exclusion criteria:
 
 • Age below 18 • Pregnant woman • Patient is unlikely/unable to awake prone positioning, or to be compliant as indicated by the treating team • Prolonged need (≥ 4 days) for HFNO, NIV or CPAP before study inclusion • Urgent need for endotracheal intubation • Invasive Mechanical Ventilation • Shock 
 ◦ Defined as need for vasopressor $\geq 0.4 \text{ mcg/kg/min}$ to maintain a mean blood pressure $\geq 65 \text{ mmHg}$ or a systolic blood pressure $\geq 90 \text{ mmHg}$ • Participation in another clinical interventional trial in the last 3 months • Previous Participation in the PROSA Trial • Long-term oxygenation therapy (LTOT) or continuous positive airway pressure (CPAP) therapy before hospital admission • Treatment with intention of palliative care and/or Do not intubate order (DNI) at time of randomization

Primary and Secondary Outcome(s)
	
Primary endpoint:
 
 • The primary endpoint will be: 
 ◦ Tracheal intubation and/or all-cause death within 28-days 
Secondary endpoints:
 
 • The secondary objectives are to compare the intervention and the control groups with respect to: 
 ◦ All-cause mortality within 28-days ◦ Tracheal intubation within 28-days ◦ Duration of achieved awake prone position (per day and total)

[figure not shown]
	
 ○ days free from invasive mechanical ventilation or non-invasive ventilation at 28 days (defined as days alive without invasive/non-invasive ventilation) ○ days free from cardiovascular organ support (including vasopressors, catecholamines and mechanical circulatory support) ○ Differences in AHRF presumed origin 
 ▪ COVID-19 ▪ Influenza ▪ Hospital acquired pneumonia ▪ Community acquired pneumonia ▪ Pneumonia in immunosuppressed individuals ○ Differences of Devices used 
 ▪ HFNO ▪ NIV ▪ CPAP ▪ Combination of the above ○ Effect on Oxygenation after awake prone positioning 
 ▪ Improvement of spO₂ ▪ Improvement in Horowitz Index ▪ Respiratory Rate ○ days alive and outside the intensive care unit at 28-days ○ days alive and outside the hospital at 28-days ○ hospital and intensive care unit length of stay ○ Organ support 
 ▪ Rate and length of RRT ▪ Need for vv-ECMO ▪ Need for va-ECMO ○ APP Related events

Trial Design
	
Investigator-initiated, prospective, randomized, open, blinded endpoint assessment (PROBE) interventional multi-center, phase 4 trial. Adaptive design with an interim analysis and re-calculation of the sample size after follow-up of 50% of the planned sample size.
 
Eligible patients will be randomized (1:1) to standard awake prone positioning or standard supine/semi-recumbent positioning alone. Randomization will be stratified by centre, mode of ventilation at randomization, as well as age (below versus equal/ above 70 years) using block randomization with varying block sizes.


Statistical analysis
	
Efficacy: The objective of the trial is to prove superiority of the intervention arm versus the control arm. The primary analysis follows from the chosen adaptive design with one unblinded interim analysis after follow-up of 50% of the patients.
 
Description of the primary efficacy analysis and population: The primary analysis will follow the intention to treat (ITT) principle in the FAS (Full Analysis Set); that includes all randomised patients, as belonging to their randomisation arm, regardless of whether awake prone positioning could be applied as intended, or whether other protocol deviations are known. All details on the analyses will be detailed in a statistical analysis plan, which will be finalised prior to inclusion of the first patient. The adaptive analysis strategy for the primary endpoint follows the Inverse Normal method to independent test statistics derived from models on per-stage data. Each analysis (interim and final) will consist of a mixed logistic regression model comparing the primary outcome "tracheal intubation or all-cause death" between random groups with age and mode of respiratory support at inclusion as fixed effects and centre as random effect in order to map the stratified randomisation scheme. One-sided significance bounds for the two analyses are 0.0026 and 0.024. Overall, an alpha of 0.025 one-sided will be spent on the primary outcome.

	
Effect size assumed for power calculation: The sample size and power calculation are based on previous knowledge, assuming a 28-day event rate of the combined endpoint in the control group of 50%, and a reduction to 35% in patients with the experimental intervention. To account for possible imprecision regarding the assumptions, an adaptive design was chosen with one interim analysis after follow-up of 50% of the planned number of patients, in order to allow stopping early for futility or efficacy and to re-estimate the sample size. Based on these assumptions and for an overall one-sided type-one error of 2.5% and statistical power of 80%, 171 patients per group (342 overall) are planned to be enrolled to prove superiority. The maximum sample size will be restricted to 513 patients.
 
Safety: Rates of adverse events and serious adverse events will be tabulated by treatment group, according to type of event and system organ class. Safety endpoints for the APP group will be analysed descriptively (event rates with two-sided 95% confidence intervals).
 
Secondary endpoint(s): Treatment effects will be calculated with two-sided 95% confidence intervals and are of descriptive nature only. Secondary outcomes will be analysed depending on the scale type, corresponding to the primary analysis. Percentage of patients meeting key safety endpoints, as well as assessment of adverse events.

Safety:	To be randomized into the trial: n = 342 To be analysed: n = 342 – intention to treat analysis Adaptive sample size: n = 342 - 513
Number of Patients	
Note: adaptive sample size (see below for details)
 
Note: recruitment will be competitively among sites (currently 20 sites planned)

Table 1. STUDY SCHEDULES

Phase of study	Screening & Randomisation	Visit 2	Visit 3
Point in time	Day 1	Day 1-3	Day 28 (± 3 days)
Informed Consent	✓		
I/E Criteria	✓		
Medical History & Demographics	✓		
Vital Signs	✓	✓	
Routine laboratory values (blood count)	✓	✓	
Routine blood gas values	✓	✓	
Parameters of oxygenation and oxygenation therapy (HFNO, NIV, CPAP)	✓	✓	
Start of Intervention (Prone Positioning) therapy	✓	✓	
Endpoints	✓	✓	✓

Figure 1. Trial Flow

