9.3.3.4 Criteria for Termination of the Study

The PROSA trial will be supervised by its Steering Committee and an independent Data Safety Monitoring Board (DSMB). All final decisions, however, regarding study termination or modification will be agreed with the Steering Committee and the independent DSMB.

No formal stopping rules will be set. An independent DSMB will monitor safety in the trial. Should safety concerns evolve, they should recommend stopping the study. Stopping the trial for efficacy or futility is an option.

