9.7.1.2.2 Statistical Analyses

All statistical analyses will be carried out by the trial statistician. To preserve the blinding of the study's biometry team until the final analysis, the unblinded interim analysis will be conducted by a separate biometry team from the same institute. Baseline variables will be described by treatment group using appropriate summary statistics.

9.7.1.2.2.1 Primary, Secondary, and Safety Endpoints

The primary efficacy analysis will be performed according to the ITT principle and will therefore be based on the FAS. The adaptive analysis strategy for the primary endpoint follows the Inverse Normal method to independent test statistics derived from adjusted mixed logistic regression models on per-stage data obtained. This strategy allows the use of conventional stopping strategies of group sequential designs. Unbiased parameter estimates and confidence intervals can be obtained by using the theory of repeated confidence intervals. In detail, the null hypothesis will be tested at overall one-sided type-one error of 2.5% with stopping boundaries according to an O'Brien and Fleming α -spending function. To account for the adaptive design of the trial, the Inverse Normal method will be used with weights $w_1=w_2=\sqrt{0.5}$ at the interim and final analysis, respectively. The test on treatment difference at each stage k ($k=1,2$) will be based on a Wald test statistic originating from a mixed logistic regression model including the treatment group (intervention versus control alone), age and respiratory status at randomization fixed effects and centre as random effect to reflect the stratified randomization. To ensure that the stage-wise test statistics are independent, the data are divided into two subsets, a first-stage and a second-stage data set.

Interim analysis:

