After follow-up of 50% of the planned patients, an interim analysis with the possibility to stop for efficacy or futility will be conducted. The treatment effect is tested using the Inverse Normal method applied to the Wald test statistic (originating from the adjusted mixed logistic regression model) at interim significance level which is determined by an O'Brien and Fleming type α -spending function. If the trial is continued to stage 2, the sample size re-calculation will be based on conditional power, with a target conditional power of 80%. After re-calculation, the sample size is adjusted with the originally calculated sample size and the maximum sample size of 342 as lower and 513 upper limit for the adjusted sample size.

Final analysis:

The second-stage data for the final analysis will be based on the Inverse Normal combination of the Wald statistics from the adjusted mixed logistic regression models of the first- and second-stage data

(with weights $w_1=w_2=\sqrt{0.5}$) at local significance level according to the α -spending function. Parameter estimates and confidence intervals are calculated based on the theory of repeated confidence intervals (RCI), where the midpoint of the two-sided RCI is used as point estimate.

Secondary endpoints: Secondary efficacy endpoints will be analysed in the FAS. Treatment effects will be calculated with two-sided 95% confidence intervals. P-values and confidence intervals derived from these analyses are of descriptive nature only. Secondary outcomes will be analysed depending on the scale type. Time-to-event outcomes will be analysed by Cox proportional hazard models including centre as frailty term. Dichotomous variables will be tested by mixed logistic regression with centre as random effect. Continuous variables will be analysed with linear mixed effects models that include the baseline determinations of the outcome and centre as random effect. Scale transformations will be considered based on the pooled data set. In further secondary analyses, the effect of the number of hours with awake prone positioning on the primary and secondary endpoints is evaluated for the intervention group.

Safety endpoints: Safety analyses will be performed in the EFS. Rates of adverse events and serious adverse events will be tabulated by treatment group, according to type of event and system organ class.

9.7.1.2.2.2 Dropouts

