9.7.1.3 Proposed Sample Size

Sample size calculation was performed with rpact 3.3.4, R version 4.2.3 [Wassmer G, Pahlke F (2023). rpact: Confirmatory Adaptive Clinical Trial Design and Analysis. R package version 3.3.4, <https://CRAN.R-project.org/package=rpact>] using the test for two proportions using the Z-test with unpooled variance. The sample size and power calculation are based on previous similar trials in COVID-19, international ICU databases, observations from small proof-of-concept studies, as well as from our own hospital-based patient information system (3, 9, 12, 14, 15). Based on these data, we estimate the relative decrease of 28-day mortality / need for tracheal intubation by our intervention compared to standard-of-care by 30%. Patients with acute hypoxemic respiratory failure on ICU, as shown by previous studies and own databases, display a 28-day event rate of the combined endpoint of 50%, so that we assume a reduction to a 28-day event rate of 35% in patients with the experimental intervention for sample size calculation (3, 9, 12, 14, 15).

Due to lack of appropriately large data sets, the current assumptions may comprise a certain imprecision. To account for this imprecision, an adaptive design was chosen with one interim analysis (O'Brien and Fleming boundary) after follow-up of 50% of the planned number of patients, in order to allow stopping early for futility or efficacy and to re-estimate the sample size. Only an independent statistician will be unblinded for this purpose and unblinded data will only be reported to the DSMB (including the DSMB statistician). The Sponsor and all other study team members stay blinded till the end of the study.

Based on these assumptions and for an overall one-sided type-one error of 2.5% and statistical power of 80%, 171 patients per group (342 overall) are planned to be enrolled to prove superiority. To avoid an unmanageably large sample size, the sample size after recalculation will be restricted to a maximum of 513 patients (chosen based on practical reasons including feasibility of enrolment and a clinically meaningful effect).

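### The printed significance bounds (0.0026 and 0.024) are those of the classical O'Brien-Fleming design, not of the O'Brien-Fleming alpha-spending function that the statistical section names, which gives 0.0015 and 0.0245

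*Protocol*

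**What the plan says.** Protocol synopsis, Statistical analysis: "One-sided significance bounds for the two analyses are 0.0026 and 0.024". The next sentence gives the total: "Overall, an alpha of 0.025 one-sided will be spent on the primary outcome". The synopsis also fixes the timing: "one unblinded interim analysis after follow-up of 50% of the patients".

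Protocol section 9.7.1.2.2.1 prints no levels and describes a method instead:
- overall: "stopping boundaries according to an O'Brien and Fleming α -spending function";
- interim: the test is made "at interim significance level which is determined by an O'Brien and Fleming type α -spending function";
- final: the combined statistic is tested "at local significance level according to the α -spending function".

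The same section sets equal Inverse Normal weights, w1 = w2 = sqrt(0.5).

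Section 9.7.1.3 (sample size) mentions no spending function. It plans "one interim analysis (O'Brien and Fleming boundary) after follow-up of 50% of the planned number of patients".

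Section 9.3.3.4 adds: "No formal stopping rules will be set". It then says that stopping for efficacy or futility is an option.

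**The concern.** The classical O'Brien-Fleming boundary and the O'Brien-Fleming-type spending function are two different designs. They resemble each other at the final look but differ clearly at an interim at half information. The synopsis gives numbers and section 9.7.1.2.2.1 gives a method. If the method does not produce the numbers, the protocol supports two decision rules for its one confirmatory test.

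At stake are the decision to stop early for efficacy, the multiplier in the repeated confidence intervals and, to a small degree, the conditional power used to re-calculate the sample size. A threshold that is open to interpretation should be settled before anyone has seen unblinded stage-1 data.

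**Working it through.** **Inputs (all from the protocol)**
- One-sided alpha 0.025; printed bounds 0.0026 and 0.024 (synopsis).
- Two looks, the first at 50% of planned patients (synopsis; 9.7.1.2.2.1); equal weights sqrt(0.5) (9.7.1.2.2.1). The stage-1 and combined statistics are then bivariate normal with correlation sqrt(0.5) = 0.7071.
- Event rates 50% and 35%, 171 per group, unpooled variance (9.7.1.3).

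**Step 1: reproduce the printed pair (classical design)**

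The bounds are C × sqrt(2) and C. Solve P(Z1 ≥ C × sqrt(2) or Z2 ≥ C) = 0.025 under the null.
- C = 1.9774, so z = 2.7965 and 1.9774.
- One-sided p = 0.00258 and 0.02400, which round to the printed 0.0026 and 0.024.
- Overall alpha of the rounded printed pair: 0.02501.

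**Step 2: the method of section 9.7.1.2.2.1 (spending function)**

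The usual form is alpha(t) = 2 × [1 − Phi(z(0.9875) / sqrt(t))].
- At t = 0.5: 2.2414 / 0.7071 = 3.1698, so alpha(0.5) = 2 × 0.000763 = 0.001525 and z = 2.9626.
- Solving for the final bound at total alpha 0.025: z = 1.9686, p = 0.02450.

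**Step 3: can another spending function explain 0.0026?**

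| Function at t = 0.5 | Interim level |
|---|---|
| 4 − 4 Phi form | 0.0008 |
| Hwang-Shih-DeCani, gamma −4 | 0.0030 |
| Hwang-Shih-DeCani, gamma −5 | 0.0019 |
| Power family, rho 3 | 0.0031 |

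None does. The usual O'Brien-Fleming-type function reaches 0.0026 only at about 55% information, with a final level of 0.0242. That is neither the planned timing nor the printed final level.

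**Step 4: consequences**

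Drift at the planned effect: 0.15 / sqrt((0.25 + 0.2275) / 171) = 2.8386.

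| | Classical | Spending |
|---|---|---|
| Overall alpha | 0.0250 | 0.0250 |
| Power, 171 per group | 80.7% | 80.9% |
| Crossing at interim, planned effect | 21.5% | 17.0% |
| Crossing at interim, null | 0.26% | 0.15% |
| Interim repeated-CI level | 99.48% | 99.69% |

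- Interim disagreement (p between 0.0015 and 0.0026): 21.5% − 17.0% = 4.5% under the planned effect, 0.1% under the null.
- Final disagreement (combined p between 0.0240 and 0.0245, no earlier stop under either rule): 0.24% and 0.05%.
- Interim interval: 2.9626 / 2.7965 = 1.059, so 5.9% wider under the spending function. Final interval: 1.9774 / 1.9686 = 1.004, so 0.4% wider under the classical design.
- Mixing the interim 0.0026 with the final 0.0245: overall alpha 0.0255.

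**Step 5: does the sample size show which design was used?**

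The inflation factors are 1.0078 (classical) and 1.0037 (spending). With unpooled variance, as section 9.7.1.3 states, 166.57 per group becomes 167.9 or 167.2, so 168 either way. With pooled null variance, 169.3 becomes 170.6 (171) or 169.9 (170). The planned 171 thus fits the classical design, but only under a variance that the protocol does not name.

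**The case against.** The best defence is that only one numeric pair is printed anywhere. The second pair is derived and depends on the usual form of the spending function, which the protocol does not write out. On this view section 9.7.1.2.2.1 merely uses a loose label, and the printed numbers govern. That may well be what was intended, but the section applies the label to the overall test, the interim level and the final level in turn, and no common variant yields the printed pair.

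Several limiting points stand:
- The point estimate is unaffected. With fixed weights, the midpoint of the two-sided repeated interval on the log-odds scale is (w1 b1/se1 + w2 b2/se2) / (w1/se1 + w2/se2), which does not contain the critical value.
- The 5.9% difference in width concerns only an interval at the interim; at the final analysis it is 0.4% in the other direction.
- The sample-size re-calculation barely moves. If conditional power is computed at the observed stage-1 effect (an assumption), 80% needs a stage-2 total of 347 or 343 at stage-1 z = 1.5, and 115 or 113 at z = 2.0. Stage 2 is limited to 342 − 171 = 171 up to 513 − 171 = 342, so both rules end at the same overall total (513 and 342).
- The sentence in section 9.3.3.4 sits beside text on safety monitoring and sets no bound. It is a secondary wording conflict.

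The SAP is due before the first randomisation and may name one rule. That would not remove the contradiction inside the protocol, which the SAP is meant to reflect.

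**Conclusion.** The point holds. The printed bounds are right for the classical O'Brien-Fleming design and wrong for the method that section 9.7.1.2.2.1 names: 0.0026 against 0.0015 at the interim, 0.0240 against 0.0245 at the end. The practical effect is small and lies almost wholly in interim p-values between 0.0015 and 0.0026. Alpha is safe as long as one pair is used whole.

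It should still be corrected, because it concerns the stopping threshold of the only confirmatory test. The result assumes an information fraction of exactly 0.5 and the usual form of the spending function; the probabilities under the planned effect also assume 50% against 35% with 171 per group. The protocol does not settle which design was meant.

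**What to change.** Before the interim analysis, name one design with its critical values in the synopsis and in sections 9.7.1.2.2.1 and 9.7.1.3:

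- **Option (a):** keep 0.0026 and 0.024. In section 9.7.1.2.2.1 replace every reference to the spending function with classical O'Brien-Fleming boundaries for two equally spaced looks, critical values 2.797 and 1.977, and use the same term in section 9.7.1.3. No number changes.
- **Option (b):** keep the spending function and state its formula. Change the synopsis to 0.0015 and 0.0245 (critical values 2.963 and 1.969), and name the spending function in section 9.7.1.3.

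Separately, reword section 9.3.3.4 so that it agrees with the efficacy boundary, for example by confining the absence of formal stopping rules to safety if that is what is meant.

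The cost is a few sentences. No extra patients are needed: 171 per group keeps power at about 81% under either option.
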